Bintralusp alfa is being developed as an immuno-oncology agent for treatment in a number of tumor types, including non-small cell lung cancer (NSCLC), biliary tract cancer (BTC), cervical cancer, and triple-negative breast cancer (TNBC).

A total of 689 participants participated in two phase I clinical trials (EMR200647-001 and MS200647-0008, as of 24 August 2018). Maximum tolerated dose (MTD) was not reached in either of the two studies at doses tested up to 30 mg/kg every 2 weeks (q2w). Each study had 1 dose-limiting toxicity (DLT) in 1 participant at the 20 mg/kg dose level. With no DLTs at other dose levels up to 30 mg/kg, bintralusp alfa at 30 mg/kg is considered tolerable. The emerging safety profile of bintralusp alfa (from EMR200647-001, MS200647-0008, MS200647-0005, MS200647-0024, MS200647-0037, MS200647-0047, and MS200647-0055) across tumor types investigated is manageable and consistent with other therapies targeting either PD-L1 or TGF- β pathways.

Treatment-emergent AEs of special interest (AESI) for bintralusp alfa are infusion-related reactions (IRRs), immune-related adverse events (irAEs), skin lesions possibly due to TGF- β inhibition and treatment-related anemia. Since 23 July 2017, IRRs (including hypersensitivity), irAEs / autoimmune disorders, and skin lesions with hyperkeratosis, keratoacanthoma, cutaneous squamous cell carcinoma possibly due to TGF- β inhibition are considered to be important identified risks with bintralusp alfa. Anemia, alterations in wound healing or

repair of tissue damage and embryofetal toxicity remained important potential risks. In addition, mucosal bleeding events are a potential risk for bintrafusp alfa.

Durable clinical activity of bintrafusp alfa was observed in a number of tumor types in the 2 Phase I studies (EMR200647-001 and MS200647-0008), specifically:

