[REDACTED], regardless of whether it is considered related or not to the study drug and that, at any dose, results in any of the following:

- results in death (fatal)
- is life-threatening (defined as an event in which the participant was at risk of death at the time of the event; it does not refer to an event which hypothetically might have caused death if it was more severe)
- requires inpatient hospitalization or causes prolongation of existing hospitalization (see **NOTE 2** below)
- results in persistent or significant disability/incapacity
- is a congenital anomaly/birth defect
- is an important medical event. Defined as a medical event(s) that may not be immediately life-threatening or result in death or hospitalization but, based upon appropriate medical and scientific judgment, may jeopardize the subject or may require intervention (e.g., medical, surgical, laboratory abnormal parameters...) to prevent one of the other serious outcomes listed in the definition above (see **NOTE 3** below)

After informed consent has been obtained, but prior to initiation of study drug, only serious adverse events caused by a protocol-mandated intervention (e.g., invasive procedures such as biopsies, discontinuation of medications) should be reported.

Seriousness is based on patient/event outcome or action criteria usually associated with events that pose a threat to a patient's life or functioning. Seriousness (not severity) serves as a guide for defining regulatory reporting obligations

NOTE 2: The following hospitalizations are not considered SAEs:

- A visit to the emergency room or other hospital department < 24 hours, that does not result in admission, except if it is considered as an important medical event or life- threatening
- elective surgery which has been planned prior to signing consent

- routine health assessment requiring admission for baseline/trending of health status (e.g., routine colonoscopy)
- admissions as per protocol for a planned medical/surgical procedure
- admission for administration of anticancer therapy in the absence of any other SAEs
- admission encountered for another life circumstance that carries no bearing on health status and requires no medical/surgical intervention (e.g., lack of housing, economic inadequacy, caregiver respite, family circumstances, administrative reason)

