13.6. Pregnancy

If, following initiation of the investigational product, it is subsequently discovered that a study participant is pregnant or may have been pregnant at the time of investigational product exposure, within 5 months after the last dose of M7824, the investigational product will be permanently discontinued.

Any pregnancy that occurs in a female partner of a male study participant should also be reported to the Fundación GECP (SLCG/GECP). Male patients will be instructed through the Informed Consent Form to immediately inform the investigator if his partner becomes pregnant during the chemotherapy treatment period or within 6 months after the last dose of chemotherapy. To allow Fundación GECP (SLCG/GECP) or designee to collect any pregnancy surveillance information from the female partner, the female partner must sign an informed consent form for disclosure of this information.

In both cases, the investigator must immediately notify to the Fundación GECP (SLCG/GECP) Pharmacovigilance Office by sending the Pregnancy form (see appendix 4) preferably by email to [contact] or by fax to the Fundación GECP (SLCG/GECP) Pharmacovigilance Office: [contact].

Follow-up information regarding the course of the pregnancy, including perinatal and neonatal outcome and, where applicable, offspring information, study discontinuation must be reported following the before procedure described during at least 1 year after child-bearing.

Any serious adverse events associated with the pregnancy (e.g., an event in the fetus, an event in the mother during or after the pregnancy, or a congenital anomaly/birth defect in the child) or abortion should be reported as a SAE.

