| Number of full-term pregnancies: _____ Number of pre-term pregnancies: _____ | | | | | |
| Previous pregnancies outcome: Normal births (n'): _____ ; Children born with defects: _____ ; Spontaneous abortion: _____ ; Induced abortion: _____ ; Ectopic pregnancy: _____ ; Others _____ (specify): _____ | | | | | |
| Are any risk factors to the current pregnancy outcome? (e.g: alcohol or substance abuse, chronic diseases, family history of birth defects...), specify: _____ | | | | | |

| | | |
|---------------------|--|--------------------------|
| PATIENT CODE | PROTOCOL CODE GECP 20/09 (BIMES) | PREGNANCY Form N° |
|---------------------|--|--------------------------|

PREVIOUS RELEVANT MEDICAL HISTORY FROM MOTHER AND/OR FATHER

PREVIOUS RELEVANT MEDICAL HISTORY (PREVIOUS DIAGNOSIS, SURGERIES, ALLERGY, CONCOMITANT DISEASES, ETC):

INFORMATION ABOUT INVESTIGATIONAL MEDICAL PRODUCT

| Trial medication (Generic name/Brand name) | Time of exposure ¹ | Daily dose | Route (IV, PO, SC...) | Start Date | Stop date or Ongoing? | Action taken with regard to trial medication ² |
|---|----------------------------------|---------------|-----------------------------|------------|--------------------------|--|
| | | | | | | |
| | | | | | | |
| | | | | | | |
| | | | | | | |
| | | | | | | |
| | | | | | | |
| | | | | | | |

¹Time of exposure: 0: pre-conception; 1: 1st trimester; 2: 2nd trimester; 3: 3rd trimester² Action taken with regard to trial medication: 0: None; 1: Reduced; 2: Delayed; 3: Delayed and reduced;
4: permanent discontinuation; 5: other (specify): _____

CONCOMITANT MEDICATION (medication took by the patient due to basal diseases or supportive clinical trial medication)

| CONCOMITANT MEDICATION (Brand name) | Daily dose | Route (IV, PO, SC...) | Onset Date | Ending date or Ongoing? | Prescription reason ³ |
|--|------------|-----------------------------|------------|----------------------------|----------------------------------|
| | | | | | |
| | | | | | |
| | | | | | |
| | | | | | |
| | | | | | |
| | | | | | |

³ Prescription reason: 1: Regular medication/baseline conditions; 2: Concomitant medication/prophylaxis; 3: Adverse Event; 4: other (specify) _____

CURRENT PREGNANCY STATUS AND OUTCOME

| | |
|--|---|

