| ONGOING  Yes  No (complete section)  Unknown  Lost to follow up: I ____ I ____ I ____ I | Newborn birth date: I ____ I ____ I ____ I (delivery date) |
| Induced abortion date: I ____ I ____ I ____ I | Delivery mode:  vaginal  caesarian  Unknown/others: |
| Spontaneous abortion date: I ____ I ____ I ____ I | Gestational weeks at birth: I ____ I |
| Ectopic pregnancy date: I ____ I ____ I ____ I | Duration of delivery: _____ hours _____ minutes |
| Others date: I ____ I ____ I ____ I | Has any prenatal testing been performed?  YES (attach anonymized report)  NO |
| PI date of awareness: I ____ I ____ I ____ I | |

2 of 3

| | | |
|--------------|-------------------------------------|-------------------|
| PATIENT CODE | PROTOCOL CODE GECP 20/09 (BIMES) | PREGNANCY Form N° |
|--------------|-------------------------------------|-------------------|

NEWBORN BABY INFORMATION

(If multiple births complete this section for each infant)

| | | | |
|--|---|--------------|--------------------------|
| Number of babies: I _____ | Gender:  Male  Female | | |
| Apgar 1 min _____ 5 min _____ 10 min _____ | Weight (Kg): | Height (cm): | Head circumference (cm): |
| If any abnormality in the newborn appeared, then answer the following question: Are there any hints that these incidences may be related to the drug exposure of the mother/father during pregnancy?  YES (complete SAE Form)  NO | General status of the newborn baby (specify): | | |
| Other relevant information about the delivery/ newborn: | | | |

INFORMATION ABOUT THE STAFF WHO ATTENDED THE DELIVERY

| | | |
|---------------|---------------|---------|
| GYNECOLOGIST: | PEDIATRICIAN: | OTHERS: |
|---------------|---------------|---------|

INFORMATION ABOUT THE SPONSOR AND THE PRINCIPAL INVESTIGATOR (PI) OF THE TRIAL

| | | | |
|---|--|--|--|
| NAME AND CONTACT DETAILS OF THE SPONSOR Fundación GECP [name] [contact] [contact] | DATE RECEIVED AND SIGNATURE OF THE SPONSOR: _____ _____ _____ | NAME AND CONTACT DETAILS OF THE PI: _____ _____ _____ | DATE AND SIGNATURE OF THE PI: _____ _____ _____ |

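### The Appendix 4 pregnancy form prompts an SAE form only for a newborn abnormality suspected to be drug-related, and never for abortion, which is narrower than sections 13.2 and 13.6

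*Combined protocol and SAP*

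**What the plan says.** **Appendix 4, newborn section.** The form states: "If any abnormality in the newborn appeared, then answer the following question". The question is "Are there any hints that these incidences may be related to the drug exposure of the mother/father during pregnancy". The YES box reads "YES (complete SAE Form"; the NO box has nothing after it. This is the only SAE prompt on the form.

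**Appendix 4, pregnancy outcome section.** Pregnancy losses are recorded as dates, for example "Spontaneous abortion date". Induced abortion and ectopic pregnancy have the same kind of field. None carries an SAE prompt or a causality question.

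**Appendix 4, exposure codes.** Time of exposure is coded "0: pre-conception; 1: 1st trimester", and so on through the trimesters.

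**Section 13.6.** Serious adverse events associated with the pregnancy are to be reported as SAEs. The sentence gives events in the fetus and the mother as examples and ends "or a congenital anomaly/birth defect in the child) or abortion should be reported as a SAE". It sets no causality condition.

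**Section 13.2.** An SAE is defined "regardless of whether it is considered related or not to the study drug". A congenital anomaly or birth defect is one of the listed seriousness criteria.

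**Section 3.3.** Embryofetal toxicity is a named risk of the drug: "repair of tissue damage and embryofetal toxicity remained important potential risks".

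**The concern.** Section 13.6 makes this form the tool for notifying a pregnancy in a patient or in a patient's partner, so it is the page a site is likely to have open when the outcome becomes known. Read literally, it asks the site to decide on causality first and to complete an SAE form only if the answer is YES. The protocol text does not allow causality to decide that.

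What is at stake is the completeness and timeliness of SAE reports for a risk that the protocol itself names. Section 13.5 asks for an SAE report within 24 hours of awareness, and a site guided only by the form might send none, or send it late. The timing of pregnancy outcomes adds to this. Section 13.5 collects SAEs within 30 days of the last dose, whereas section 13.6 follows a pregnancy for at least 1 year after birth. An outcome may therefore arrive when the site is no longer routinely completing SAE forms for that patient.

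**Working it through.** No arithmetic applies. The check sets what the form prompts against what the text requires, outcome by outcome.

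| Outcome | Appendix 4 form | Sections 13.2 and 13.6 |
|---|---|---|
| Birth defect, drug relation suspected | SAE form prompted | SAE |
| Birth defect, drug relation not suspected | No instruction | SAE: named in 13.6, a seriousness criterion in 13.2, relation irrelevant |
| Spontaneous abortion | Date only | SAE: 13.6 names abortion |
| Induced abortion | Date only | SAE: 13.6 names abortion and does not separate induced from spontaneous |
| Ectopic pregnancy | Date only | Not named in 13.6; an SAE if it is a serious event in the mother or fetus |
| Newborn abnormality that is neither a birth defect nor otherwise serious | SAE form prompted on YES only | Not named as an SAE in 13.6 |

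**Step 1.** In the first row the form and the text agree.

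**Step 2.** In the second, third and fourth rows the text requires an SAE report and the form does not prompt one. These rows are the inconsistency.

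**Step 3.** The last two rows mark where it stops. Section 13.6 does not make every ectopic pregnancy or every newborn abnormality an SAE; seriousness under 13.2 still has to be met.

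**Step 4.** The causality question refers to exposure during the pregnancy, yet the form's own code 0 is exposure before conception. If the mother's or father's dosing ended before conception, the literal answer is NO even when a drug effect is suspected. The NO box then gives no SAE instruction.

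**Step 5.** Where the causality-independent rule is written also matters. Section 13.6 contains no causality condition but does not say in words that causality is irrelevant; the explicit statement is in 13.2. The conflict rests on reading the two sections together, which is the natural reading because 13.6 uses the term that 13.2 defines.

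**The case against.** The strongest reply is that silence on a form does not cancel a duty in the protocol. The NO box does not tell the site to withhold an SAE report, and 13.6 still binds the investigator. That is correct. The point is a missing and misleading prompt, not a contrary instruction.

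The protocol also has safeguards. Section 13.6 requires the pregnancy form to go immediately to the sponsor's pharmacovigilance office. Section 13.2 says pregnancy itself must be handled as an SAE. Section 13.5 provides for pregnancy reports to be passed on, with periodic reconciliation. These stand, and they limit the consequence to the separate SAE report.

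A reader might infer more than the documents support:

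- *That the event would be lost, or that a missed case could be all the trial's information on this risk.* The abortion date or newborn abnormality is on the pregnancy form that the sponsor receives.
- *That expectedness review would be lost.* Under 13.2, expectedness is assessed only for SAEs that the investigator considers related. An anomaly considered unrelated would have no such review even with an SAE form.
- *That the event would drop out of an SAE tabulation.* Section 16 describes no such tabulation.
- *That the eCRF has the same gap.* Section 15 says the paper pregnancy form is used only when the eCRF is unavailable, although 13.6 also describes sending the form directly. The eCRF page is not in the documents, so this is unknown.

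It can also be said that the exposure wording is a matter of taste, because timing is recorded elsewhere on the form. That is true of the data captured, but the SAE prompt hangs on the question and not on the exposure code.

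**Conclusion.** The inconsistency is real and minor. The form's single SAE prompt depends on suspected drug relation and omits abortion; sections 13.2 and 13.6 impose no such condition and include abortion. The consequence is that a separate SAE report could be omitted or delayed for a birth defect thought unrelated or for an abortion. The event would still be known to the pharmacovigilance office.

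Few cases are expected. That is an assumption, because the documents give no pregnancy rate, but it is plausible with 47 patients, pregnancy excluded at entry, contraception required and pregnancy testing every 4 weeks during treatment. No endpoint, analysis or decision rule depends on this form. The conclusion also assumes that some sites would take the form as complete guidance without returning to 13.6. It makes no claim about the eCRF page.

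**What to change.** Replace the conditional prompt on the form with wording such as: *Congenital anomaly/birth defect, spontaneous or induced abortion, or any other serious event in the mother, fetus or child (including ectopic pregnancy when it meets a seriousness criterion): complete the SAE Form irrespective of causality (sections 13.2 and 13.6).* Place it so that it covers the abortion and ectopic fields as well as the newborn section.

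Keep the causality question as a separate item that triggers nothing, and reword it to ask about exposure *before conception or during pregnancy*, which matches exposure code 0.

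Check that the eCRF pregnancy page says the same, and change it only if it does not.

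The wording should not extend to every newborn abnormality or every ectopic pregnancy, since that would create a new mismatch with 13.6. The cost is an edit to one form, possibly one eCRF page, and at most a few extra SAE forms. No visits or procedures are added.
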